***Fibrotic and Inflammatory Biomarkers:***

The following parameters will be measured at select study visits as per the Schedule of Assessments:

- Fibrotic and inflammatory biomarkers (granulocyte colony stimulating factor [G-CSF], monokine induced by gamma interferon [MIG], fibroblast growth factor-2 [FGF-2], interleukin(IL)-4, IL-10, lymphotoxin- $\alpha$ / tumor necrosis factor beta [TNF- $\beta$ ], leptin, IL-6, IL-1 $\beta$ , tumor necrosis factor alpha [TNF- $\alpha$ ], TGF- $\beta$ 1, matrix metalloproteinase 9 [MMP-9], tissue inhibitor of matrix metalloproteinase 1 [TIMP-1], monocyte chemoattractant protein-1 [MCP-1]).

These data may be reported separately in a supplementary report to the main Clinical Study Report.

***Endpoints for the Study are Defined as Follows:***

Primary Endpoint:

- Safety and tolerability (AEs, physical examination, vital signs, ECGs, clinical laboratory parameters [hematology, serum chemistry, coagulation, and urinalysis], and concomitant treatments).

Secondary Endpoint:

- Efficacy:
  - Limb water content, by BIS.
  - Limb volume (perometry).
  - Tissue dielectric constant (MoistureMeterD).
  - Tissue firmness (tonometry/SkinFibroMeter).
  - Visual analog scales for pain, swelling, discomfort, and function.
- Infection:
  - Cellulitis.

- Lymphangitis.
- Health-related QoL:
  - LYMPH-Q- Upper Extremity Module ([Appendix 2](#)).
  - LYMQOL ([Appendix 3](#)).
- Population PK parameters.
- Fibrotic and Inflammatory biomarkers:
  - Fibrotic and inflammatory biomarkers (G-CSF, MIG, FGF-2, IL-4, IL-10, lymphotoxin $\alpha$ /TNF- $\beta$ , leptin, IL-6, IL-1 $\beta$ , TNF- $\alpha$ , TGF- $\beta$ 1, MMP-9, TIMP-1, MCP1).

**Statistical Methods:**

A statistical analysis plan (SAP) will be written that will describe, in greater detail, the analyses to be performed for each part. The sections below provide a summary of the general approach to the analysis. The analysis is consistent with the study design. Note that this study is not hypothesis testing but rather hypothesis-generating, and thus conclusions regarding outcomes will not be based on inferential tests but rather descriptive outcomes, magnitude of treatment effects, and a preponderance of evidence regarding the risk-benefit profile of LYT-100.

*Sample Size*

Approximately 50 patients with secondary lymphedema will be randomized in a 1:1 ratio to LYT-100 or placebo, as part of this early development and exploratory study of LYT-100. Formal sample size calculations will not be performed; rather, the sample size selected should be adequate for preliminary evaluation of safety, tolerability, efficacy signaling, PK, and fibrotic and inflammatory biomarker parameters in the targeted patient population.

*General Statistical Plan*

The baseline for all variables will be the last measurement obtained prior to the patient receiving the first dose of study treatment.

Patient disposition (including the number and percent of patients who are enrolled, who receive treatment, who prematurely discontinue and reasons for discontinuation, and who complete the study) will be tabulated by treatment group. Summary statistics for days of exposure and concentration of exposure will be provided by treatment group.

AEs, concomitant medications, clinical laboratory findings, physical examinations, ECGs, and vital signs for each patient will be tabulated or summarized descriptively, where appropriate.

Demographic information will be presented for each patient and summarized. Treatment-emergent adverse events (TEAEs) and laboratory, vital signs, and ECG parameters will be summarized. In addition, change from baseline will be summarized for laboratory and vital sign parameters. Shift tables will also be provided for clinical laboratory results. ECG results will be classified as normal and abnormal and summarized. ECG results for QTcF will also be classified as < 450 msec, 450 to 500 msec or > 500 msec. Changes in physical exams will be described.

*Study Populations*

- The Safety Population is defined as all patients who receive LYT-100, or Placebo.
- The Full Analysis Set (FAS) population is defined as all randomized patients who received at least one dose of double-blinded study medication and had at least one post-baseline efficacy assessment. All efficacy endpoints will be assessed using this population.
- The Pharmacokinetic Population (PP) is defined as all patients who receive the double-blinded study medication and for whom an evaluable concentration-time profile is available for the determination of at least one PK variable. Patients with emesis after consuming study

medication will be assessed on a case-by-case basis for eligibility for inclusion in the PK population. In general, patients who vomit after at least 2 half-lives of the given medication will be included in the PK population (as  $C_{max}$  will presumably be reached by that time).

- The Fibrotic and Inflammatory Biomarker Population is defined as all patients who receive the double-blinded study medication and who provide biomarker and lymphedema assessment data.

#### *Study-Specific Requirements*

Analysis of clinical assessments and potential progression or disease will be explored. Comparisons between LYT-100 and placebo will be based on clinical interpretation of effect, magnitudes of effect, and a preponderance of evidence. Estimates of changes over time from these data may be used to power future clinical studies.

The primary endpoints are safety (clinical laboratory parameters, vital signs, ECGs, and spontaneously reported AEs) and tolerability of the double-blinded study medication. Secondary endpoints include efficacy (lymphedema assessments, infection, and health-related QoL), population PK, and fibrotic and inflammatory biomarkers of the double-blinded study medication.

Change from baseline to each post-baseline visit (through Week 26; on-treatment effect) on the following endpoints will be calculated for the following endpoints: fibrotic and inflammatory biomarkers (G-CSF, MIG, FGF-2, IL-4, IL-10, lymphotoxin  $\alpha$ /TNF- $\beta$ , leptin, IL-6, IL-1 $\beta$ , TNF- $\alpha$ , TGF- $\beta$ 1, MMP-9, TIMP-1, MCP-1), limb water content (BIS), limb volume (truncated cone tape measure and/or perometry), tissue dielectric constant (MoistureMeterD), tissue firmness (tonometry/SkinFibroMeter), visual analog scales (pain, swelling, discomfort, and function), and QoL (LYMPH-Q, LYMQOL). For select efficacy outcomes, use of a mixed model for repeated measures (MMRM) will be used to provide model-based estimates of changes over time in each of these outcomes. Descriptive statistics will also be provided at each time point. Details for the model (including covariates to be included) will be provided in the SAP.

Data for all endpoints will be tabulated, displayed graphically, or summarized descriptively, as appropriate. No formal hypothesis testing will be performed.

### 3. STUDY SCHEDULE OF ASSESSMENTS

**Table 5. Schedule of Events**

Study Day	Screening	Baseline	LYT-100 Patient Cohort Double-Blind Treatment Phase  (N = approximately 50) 										Final Safety Visit
	Day -28 to Day -2	Day -1	Day 1	Week 1	Week 2	Week 4	Week 8	Week 12	Week 16	Week 20	Week 23	Week 26 or Early Termination 	Week 30 (28 days from last dose)
Study Drug			Dose	Dose	Dose	Dose	Dose	Dose	Dose	Dose	Dose	D/C Dose	n/a
+/- Days Allowable		+/-0	+/-0	+/-2	+/-3	+/-3	+/-3	+/-3	+/-3	+/-3	+/-3	+/-3	+/-3
Visit	1	2	(no visit)	3	Phone Call	4	5	6	7	8	Phone Call	9	10
Outpatient Clinic Visit	X	X	(no visit)	X	Phone Call	X	X	X	X	X	Phone Call	X	X
Informed Consent 	X												
Eligibility Assessment	X	X											
Demographics	X												
Medical History 	X												X
12-lead ECG (QTcF) 	X			X				X				X	X
Physical Exam 	X			X				X				X	X
Vital Signs (Height, Weight, BMI, Body Temp, HR, BP, RR) 	X	X		X		X	X	X	X	X		X	X
Bioimpedance 		X		X		X	X	X	X	X		X	
Limb Volume 		X		X		X	X	X	X	X		X	
MoistureMeterD 		X		X		X	X	X	X	X		X	
Tonometry/Skin FibroMeter 		X		X		X	X	X	X	X		X	
Visual Analog Scales		X		X		X	X	X	X	X		X	
LYMPH-Q		X		X		X	X	X	X	X		X	
LYMQOL		X		X		X	X	X	X	X		X	

	Screening	Baseline	LYT-100 Patient Cohort Double-Blind Treatment Phase  (N = approximately 50) 										Final Safety Visit
Study Day	Day -28 to Day -2	Day -1	Day 1	Week 1	Week 2	Week 4	Week 8	Week 12	Week 16	Week 20	Week 23	Week 26 or Early Termination 	Week 30 (28 days from last dose)
Study Drug			Dose	Dose	Dose	Dose	Dose	Dose	Dose	Dose	Dose	D/C Dose	n/a
+/- Days Allowable		+/-0	+/-0	+/-2	+/-3	+/-3	+/-3	+/-3	+/-3	+/-3	+/-3	+/-3	+/-3
Visit	1	2	(no visit)	3	Phone Call	4	5	6	7	8	Phone Call	9	10
Sparse PK Blood Samples 				X		X	X	X	X	X		X	
Concomitant Medication 	X	X		X	X	X	X	X	X	X	X	X	X
Adverse Events 	X	X		X	X	X	X	X	X	X	X	X	X
Pregnancy test 	Urine	Urine						Urine				Urine	
FSH 	X												
Genotyping 		X											
Hematology 	X			X		X		X				X	X
Chemistry 	X			X		X	X	X	X	X		X	X
Coagulation 	X			X		X		X				X	X
Urinalysis	X	X		X		X		X				X	X
Urine Cotinine, drug screen & alcohol breath test	X	X										X	
Exploratory Inflammatory Biomarkers 		X		X			X		X			X	
Review Patient Diary 		X		X		X	X	X	X	X	Week 26 diary reminder	X	
Study Drug Dispensing and Drug Accountability		X	(first dose taken)	X		X	X	X	X	X	(cont. dosing)	(acct. only)	n/a
Participant Interview 	X												X

Abbreviations: AE = adverse event; ALT = alanine aminotransferase; APTT = activated partial thromboplastin time; AST = aspartate aminotransferase; BID = twice a day; BMI = Body Mass Index; BP = blood pressure; D/C = discontinue; ECG = electrocardiogram; FSH = follicle-stimulating hormone; HR = heart rate; LYMPH-Q- Upper Extremity Module;; LYMQOL = Lymphedema Quality of Life Tool, Arm; n/a = not applicable; PK = pharmacokinetics; RR = respiratory rate.

1. Double-blind treatment is either LYT-100, 750 mg BID or matching placebo by mouth, on an outpatient basis.
2. Early termination is defined as premature discontinuation t
3. Informed consent must be documented before any study-specific Screening procedures are performed.
4. Medical history includes breast cancer, surgical, radiation and therapy history. It should be updated as needed at the final safety visit (# 11).
5. ECG are to be conducted 2.5 hours (+/- 15 minutes) after the morning study drug dose on Week 1 and Week 12 visits.
6. A full physical exam will be conducted at the Screening and final safety visits. Symptom directed physical examinations will be performed at all other indicated visits.
7. Height is collected at baseline while vital signs, weight, and BMI are collected only one time at each designated visit.
8. All breast cancer-related lymphedema (BCRL) assessments should be done toward the end of the study visit. If the patient is using a compression sleeve, it should be removed upon arrival at the study visit and not placed back on until all assessments for the study visit are collected. Where possible, BCRL assessments may be conducted at the Screening (in addition to baseline) visit so that patients do not fail eligibility at baseline.
9. Pharmacokinetic samples are collected at each visit except Screening, baseline, and post-treatment phase. Last dose taken prior to blood collection will be recorded. Population PK will be grouped into the following timepoint ranges post-study med dose administration: Hour 0, Hour 1 to < 2, Hour 2 to < 4, Hour 4 to < 8, Hour 8 to 12.
10. Concomitant medications include all medications taken 30 days prior to the Screening visit.
11. Adverse events include medical conditions such as infections (e.g., cellulitis and lymphangitis) starting or worsening after LYT-100 or placebo administration. All other medical conditions reported around Screening and Baseline prior to study treatment administration will be reported as pre-treatment AEs.
12. Not required for amenorrhoeic female patients (see below); if a urine pregnancy test is positive, it must be confirmed by a serum pregnancy test.
13. Amenorrhoeic female patients only; postmenopausal status will be confirmed through testing of FSH levels ( $\geq 40$  IU/mL).
14. Patients will provide blood samples at baseline (Day -1) for the determination of CYP1A2, CYP2C9, CYP2C19, and CYP2D6 genotyping – Sample to be obtained on Day -1 of the first period only. Patients are required to provide consent for genotyping.
15. Hematology includes complete blood count and differential.
16. Serum chemistry includes glucose, total protein, albumin, electrolytes (sodium, potassium, chloride, total CO2), calcium, phosphorus, magnesium, uric acid, bilirubin (total, direct), ALT or AST, alkaline phosphatase, creatinine, blood urea nitrogen, creatine phosphokinase (CPK). Liver Function Tests (LFTs) will be collected at each visit and includes bilirubin (total, direct), ALT or AST, and alkaline phosphatase.
17. Coagulation includes international normalized ratio (INR), prothrombin time and APTT.
18. Inflammatory markers include: G-CSF, MIG, FGF-2, IL-4, IL-10, lymphotoxin- $\alpha$ /TNF- $\beta$ , leptin, IL-6, IL-1 $\beta$ , TNF- $\alpha$ , TGF- $\beta$ 1, MMP-9, TIMP-1, MCP-1.
19. Patient completes the Patient Diary starting 1 week prior to each study visit and returns the diary at the end of the week while attending the study visit.
20. Relative limb volume is measured by perometry. Perometry is a non-invasive technique involving a Perometer (Pero-System), which uses infrared light to scan a limb and obtain measurements of the limb's circumference. The truncated cone tape measure method can be used as a backup if the Perometer is unavailable, or not working at time of the patient visit.
21. Patients will be asked to participate in interviews to discuss their Breast Cancer related Lymphedema either during screening (i.e. to include subjects that are deemed ineligible and not able to participate in the study) or at the end of the treatment period (Week 30 for those that are deemed eligible and complete study treatment)

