## 10. SELECTION AND WITHDRAWAL OF PATIENTS

### 10.1. Patient Inclusion Criteria

To be eligible for this study, patients have to meet *all* of the following inclusion criteria:

1. Provides written Ethics Committee approved informed consent prior to any study procedures.
2. Female or male aged  $\geq 18$  years old at the time of informed consent.
3. At least 6 months and no more than 15 years since the most recent type of surgery related to breast cancer including sentinel lymph node biopsy or excision/clearance, axillary lymph node dissection, or any other type of surgery excluding FNA biopsy at the time of study screening. No intention to have breast reconstructive surgery, nipple reconstruction, and/or tattooing during the course of the study.
4. At least 3 months since completion of any neoadjuvant therapy, adjuvant chemotherapy, intravenous biologic therapy (e.g., trastuzumab and pertuzumab), radiotherapy, and/or any investigational adjuvant therapy at the time of study Screening.
5. At least 3 months since initiation of anti-hormonal oral adjuvant therapy as well as goserelin and/or adjuvant zoledronic acid.
6. Diagnosis of primary breast cancer, and without evidence of local, locoregional and/or distant recurrence of breast cancer for at least 6 months since completion of adjuvant therapy (excluding anti-hormonal therapy regimens), as determined at Screening and Baseline.
7. Documented evidence of pitting edema in one arm for at least 3 months and also at Screening, and at least one of the following:
  - a. Increase in relative limb volume of between 10% to 25% as measured by perometry or the truncated cone method of circumferential tape measurement compared to any prior documented measurement or relative to measurement of non-affected arm.
  - b. A bioimpedance measure of  $> 10$  at baseline visit or a change from pre-surgical measure of  $> +6.5$  L-Dex at Baseline visit; or
  - c. Overt signs of lymphedema in the arm clinically indicating Lymphedema Stage I or II and/or confirmed by asymmetry  $> 2$  via LymphaScan (TDC) in swell spot.
8. Receiving standard of care compression or agreeable to using care compression, i.e., sleeves and/or pumps and/or manual lymphatic drainage, or no compression care and/or no manual lymphatic drainage  $\geq 4$  weeks prior to Screening and throughout the study.

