  16. WOCBP must be non-pregnant and non-lactating, and must use an acceptable, highly effective double contraception or be abstinent from heterosexual intercourse from Screening until study completion, including the follow-up period (please see Section 10.4.3 for acceptable methods of contraception). WOCBP must have a negative pregnancy test at Screening and Day 1 and be willing to have additional pregnancy tests as required throughout the study. Women not of childbearing potential must be postmenopausal for  $\geq 12$  months or be surgically sterile, including a hysterectomy with retention of ovary function is permitted. Postmenopausal status will be confirmed through testing of FSH levels  $\geq 40$  IU/mL at Screening for amenorrhoeic female patients.
  17. Male patients must be surgically sterile ( $> 30$  days since vasectomy with no viable sperm), abstinent, or if engaged in sexual relations with a WOCBP, the patient and his partner must be surgically sterile (e.g., tubal occlusion, hysterectomy, bilateral salpingectomy, bilateral oophorectomy) or using an acceptable, highly effective contraceptive method from Screening until study completion, including the follow-up period and an additional 12 weeks after the last dose (please see Section 10.4.3 for acceptable methods of contraception).
  18. Males must not donate sperm for at least 90 days after the last dose of study drug.
  19. Partners of male patients and female patients will report pregnancy occurring within 90 days from cessation of study medication.

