#### **10.4.3. Contraception**

No estrogen preparations (e.g., oestradiol, ethinylloestradiol) are to be used throughout the trial for contraception, hormone replacement therapy, or menopausal replacement therapy.

Acceptable, highly effective double contraception is defined as a condom AND one other form of the following:

- Established hormonal contraception (oral contraceptive pills [OCPs], long-acting implantable hormones, injectable hormones) except for preparations containing oestradiol, ethinylloestradiol
- A vaginal ring or an intrauterine device (IUD)
- Documented evidence of surgical sterilization at least 6 months prior to Screening (e.g., tubal occlusion, hysterectomy, bilateral salpingectomy, or bilateral oophorectomy for women or vasectomy for men [with appropriate post-vasectomy documentation of the absence of sperm in semen] provided the male partner is a sole partner).

Women not of childbearing potential must be postmenopausal for  $\geq 12$  months. Postmenopausal status will be confirmed through testing of FSH levels  $\geq 40$  IU/mL at Screening for amenorrhoeic female patients. Females who are abstinent from heterosexual intercourse will also be eligible.

Periodic abstinence (e.g., calendar, ovulation, symptothermal, post-ovulation methods) and withdrawal are not considered highly effective methods of birth control. Patient complete abstinence for the duration of the study and for 1 month after the last study treatment is acceptable.

Female patients who are in same sex relationships are not required to use contraception.

Males must be surgically sterile ( $> 30$  days since vasectomy with no viable sperm), abstinent, or if engaged in sexual relations with a WOCBP, the patient and his partner must be surgically sterile (e.g., tubal occlusion, hysterectomy, bilateral salpingectomy, bilateral oophorectomy) or using an acceptable, highly effective contraceptive method from Screening until study completion, including the follow-up period. Acceptable methods of contraception include the use of condoms and the use of an effective contraceptive for the female partner that includes: OCPs, long-acting implantable hormones, injectable -hormones, a vaginal ring, or an IUD. Patients with same sex partners (abstinence from penile-vaginal intercourse) are eligible when this is their preferred and usual lifestyle.

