### **13.7. Visit 6 (Week 12, ± 3 days)**

Patients will attend an onsite visit at the CRU. The following assessments will be performed:

- Visual analog scales
- LYMPH-Q
- LYMQOL
- 12-lead ECG (QTcF), to be collected 2.5 (+/- 15 minutes) after the morning study drug dose
- Symptom directed physical exam
- Concomitant medication
- Adverse events
- Review patient diary
- Bioimpedance
- Limb volume
- MoistureMeterD
- Tonometry/Skin FibroMeter
- Vital signs (weight, BMI, body temperature, HR, BP, RR)
- Study drug dispensing and drug accountability
- Sparse PK blood samples
- Urine pregnancy test: Not required for amenorrhoeic female patients; if a urine pregnancy test is positive, it must be confirmed by a serum pregnancy test.
- Blood hematology
- Serum chemistry (including LFT panel)
- Coagulation
- Urinalysis

Patients will be provided with a quantity of study medication sufficient for self-administration BID until Visit 7.

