#### **15.1.6.7. Pregnancy Testing**

A urine pregnancy test will be performed at the time points indicated in the Schedule of Assessments for WOCBP only. If a urine test is positive, a serum test will be performed immediately for confirmation.

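### Pregnancy tests are waived for amenorrhoeic women although the protocol elsewhere requires them by childbearing potential, and two passages end male contraception at different times

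*Combined protocol and SAP*

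**What the plan says.** **Who is exempt.** Footnote 12 to Table 5 applies to all four scheduled pregnancy tests and reads "Not required for amenorrhoeic female patients (see below". The pointer leads to footnote 13, on FSH testing of amenorrhoeic women. Section 13.1 (Screening) has the same waiver and pointer. Sections 13.2 (Day -1), 13.7 (Week 12) and 13.11 (Week 26 or early termination) have the waiver without the pointer; Section 13.7, for example, has "Urine pregnancy test: Not required for amenorrhoeic female patients".

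**Who must be tested.** Inclusion 16 (Section 10.1, repeated in the synopsis) says of women of childbearing potential: "WOCBP must have a negative pregnancy test at Screening and Day 1". It also asks them to accept further tests as needed. Section 7.5 repeats the requirement for a negative test at Screening and before the first dose. Section 15.1.6.7 says: "A urine pregnancy test will be performed at the time points indicated in the Schedule of Assessments for WOCBP only". None of these makes an exception for amenorrhoea.

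**Who is not of childbearing potential.** Inclusion 16 recognises women postmenopausal for at least 12 months, with FSH of at least 40 IU/mL at Screening as confirmation if they are amenorrhoeic. It also recognises surgically sterile women, including those with a hysterectomy and retained ovaries.

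**Male contraception.** Inclusion 17 carries the duty through "including the follow-up period and an additional 12 weeks after the last dose". Section 10.4.3 asks for "using an acceptable, highly effective contraceptive method from Screening until study completion, including the follow-up period" and adds nothing after that. The follow-up visit (Visit 10) is 28 ± 3 days after treatment ends.

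**The concern.** One safety check is governed by two different populations. The operational text that site staff follow at each visit (Table 5 and Section 13) selects women by amenorrhoea. The eligibility criteria and the laboratory section select them by childbearing potential. The two groups overlap but are not the same, and the protocol does not say which passage prevails.

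Exclusion 15 bars pregnant patients, and the urine test is the scheduled objective check on that exclusion before dosing and on pregnancy during 182 days of treatment. If a site follows Table 5, a woman whom the protocol itself classes as of childbearing potential may be dosed, or continue on treatment, without the test that other sections require.

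For men, a site can follow the restrictions in Section 10.4.3 exactly and still breach Inclusion 17.

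**Working it through.** No statistical figure is involved. The check sets the passages side by side and converts the time windows to days.

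**Step 1: the four tests.**

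| Time point | Waiver in | Pointer to FSH | Rule by childbearing status that stands apart from the schedule |
|---|---|---|---|
| Screening | footnote 12, 13.1 | both places | Inclusion 16, 7.5 |
| Day -1 | footnote 12, 13.2 | footnote only | Inclusion 16 and 7.5 (they name Day 1) |
| Week 12 | footnote 12, 13.7 | footnote only | only the as-needed clause of Inclusion 16 |
| Week 26 or early termination | footnote 12, 13.11 | footnote only | only the as-needed clause of Inclusion 16 |

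The waiver covers 4 of 4 tests. Table 5 shows no visit on Day 1, so in practice the pre-dose requirement falls on the Day -1 test, where Section 13.2 carries the waiver unqualified. At Weeks 12 and 26 the fixed requirement is Section 15.1.6.7, which takes its time points from the schedule and so leads back to footnote 12.

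**Step 2: does the FSH pointer close the gap?** Footnote 13 says that menopause will be confirmed by FSH in amenorrhoeic women. It does not make the waiver depend on the result. No passage says what follows if FSH is below the threshold. FSH is drawn only at Screening.

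**Step 3: apply both rules to each kind of amenorrhoeic woman.**

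| Amenorrhoeic woman | Childbearing potential under Inclusion 16 | Literal wording of footnote 12 | Agreement |
|---|---|---|---|
| Postmenopausal at least 12 months, FSH at least 40 IU/mL | no | exempt | yes |
| Surgically sterile, including hysterectomy with ovaries retained | no | exempt | yes |
| Not sterile, postmenopausal for less than 12 months | yes | exempt | **no** |
| Not sterile, FSH below 40 IU/mL | yes (menopause not confirmed) | exempt | **no** |

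The contradiction is confined to the last two rows.

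**Step 4: male contraception, in days after the last dose.**
- Inclusion 17: 12 weeks × 7 = 84 days.
- Section 10.4.3: the follow-up visit at 28 ± 3, that is 25 to 31 days.
- Difference: 84 - 28 = 56 days; over the visit window, 84 - 31 = 53 to 84 - 25 = 59 days.

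**Step 5: pregnancy reporting.** Inclusion 19 says: "Partners of male patients and female patients will report pregnancy occurring within 90 days from cessation of study medication". Beyond the last scheduled contact this leaves 90 - 31 = 59 to 90 - 25 = 65 days.

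**The case against.** The strongest reply is that the protocol already requires the test. A woman of childbearing potential without a negative result at Screening and Day 1 fails Inclusion 16, Section 7.5 says the same, and Section 15.1.6.7 ties the scheduled tests to childbearing status. The pointer in footnote 12 also suggests that amenorrhoeic was shorthand for women whose menopause is being confirmed. On this view only the wording is loose.

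Much of this stands. A reader might infer that these women will go untested. The documents do not support that: they permit a missed test but do not settle on omitting it. The reply does not remove the contradiction, however, because the pointer sets no condition, three visit lists omit it, and Section 15.1.6.7 refers back to the schedule that contains the waiver.

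Other tempting readings also go too far:

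- **Every amenorrhoeic woman with low FSH is wrongly exempt.** No: hysterectomy with retained ovaries counts as sterile.
- **Women only 3 months past chemotherapy are the group at risk.** Inclusion 4 has a 3-month limit, but Inclusion 6 also requires at least 6 months since adjuvant therapy, anti-hormonal regimens aside. Inclusion 3 requires at least 6 months since the latest surgery. Inclusion 5 ("At least 3 months since initiation of anti-hormonal oral adjuvant therapy as well as goserelin and/or adjuvant zoledronic acid") does admit women on goserelin, but the documents say nothing about its effect on periods.
- **A woman whose periods stop because she is pregnant is exempt.** The bare words allow it, but she remains of childbearing potential under Section 15.1.6.7, and the reading is strained.
- **A pregnancy could stay undetected for 26 weeks.** That assumes that the required double contraception fails, that no as-needed test is done, and that nothing emerges at nine on-treatment contacts.
- **The pregnancy-reporting windows conflict.** There is one window, 90 days, worded alike in the synopsis and Section 10.1. Reporting is placed on patients and partners, so it does not need a visit. Section 16.4 requires follow-up of all pregnancy outcomes, even after discontinuation.

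On male contraception it can be said that Inclusion 17 cites Section 10.4.3 only for methods, and that a patient who meets the longer duty satisfies both passages. True, but Section 10.4.3 states its own end point, and staff who rely on it would stop earlier.

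**Conclusion.** Two internal contradictions stand.

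1. The waiver applies to all four scheduled pregnancy tests and is keyed to amenorrhoea. The duty to test is keyed to childbearing potential. Amenorrhoeic women who are neither surgically sterile nor confirmed postmenopausal fall under both rules and may go untested, especially at Weeks 12 and 26. The documents do not say how many of the approximately 50 patients this would be, so no frequency is claimed.
2. Male contraception ends at 84 days after the last dose in one passage and at about 28 days in the other, a gap of about 56 days (53 to 59). This assumes that study completion in Section 10.4.3 means the follow-up visit.

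The 90-day pregnancy-reporting window is worth noting but is not a contradiction: it runs 59 to 65 days past the last scheduled contact and relies on self-report.

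The point should be corrected because it concerns operative safety text. It does not affect the statistical analysis.

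**What to change.** - Reconcile the waiver wording in Table 5 footnote 12 and Sections 13.1, 13.2, 13.7 and 13.11 with the definition of childbearing potential in Inclusion 16 and with Sections 7.5 and 15.1.6.7, so that one population governs the test at all four time points. State what applies when an amenorrhoeic woman's menopause is not confirmed. The clinical rule itself is for the sponsor to decide.
- Reconcile Inclusion 17 (synopsis and Section 10.1) with Section 10.4.3 on when male contraception ends.
- No change is required for the 90-day reporting window.

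The cost is amendment wording in one footnote, four visit lists and one contraception passage. If the sponsor's decision means that more women are tested, add a few urine tests, at most four per woman, at visits that already take place.
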